5.2 Pharmacokinetic Evaluation (if applicable)

Not applicable

5.3 Safety Evaluations

Not applicable

6 STATISTICAL CONSIDERATION

6.1 Primary Endpoint

Informed Decision-Making

6.2 Secondary Endpoint

See Table 1 appended

6.3 Statistical Methods

Preliminary Analyses: Characteristics of study participants will be presented, stratified by study group, using means and percentages, depending on the measurement properties of the variables involved. Statistical comparisons will be made using linear regression models for continuous variables and chi-square tests for categorical variables. All data analyses will be performed using SAS PC, version 9.4 (SAS Institute, Cary, NC).

Primary Analyses: The primary outcome variable is Informed Decision-Making assessed at the 6-month follow-up. The investigators will test the following hypotheses using logistic regression methods.

1. Participants will be more likely to meet the criteria for Informed Decision-Making at the 6-month follow-up if they were assigned to receive written medication information via the DrugFactsBox[®] format compared to the Other CMI format.
2. Participants will be more likely to meet the criteria for Informed Decision-Making at the 6-month follow-up if they were assigned to receive gist reasoning training, delivered via the SMART Program, compared to those who were not assigned to receive this training.
3. Participants will be more likely to meet the criteria for Informed Decision-Making at the 6-month follow-up if they were assigned to receive medication information via the DrugFactsBox[®] format **combined with** gist reasoning training, delivered via the SMART Program, compared to individuals in the other three groups.

The regression model will control for Informed Decision-Making at baseline (0=Did not meet criteria for Informed Decision-Making, 1=Met criteria for Informed Decision-Making) and indicator variables for each intervention indexing whether the participant was assigned to SMART Training (0=No, 1=Yes) and the DrugFactsBox[®] group (0=No, 1=Yes). In separate regression models, the investigators will also test three 2-way interactions. The first interaction will assess whether the effects of the two interventions are dependent of one another (Hypothesis 3). The other interaction terms will assess whether the effects of each intervention varies as a function of whether participants met the criteria for Informed Decision-Making at baseline. Statistical significance will be evaluated with alpha (2-tailed) set at 0.05. When significant interaction terms are observed, the investigators will use stratified analyses to examine the nature of the interaction.

In the main analysis, the investigators will use an *intention-to-treat* strategy, with individuals included in the analysis based on random group assignment, without regard to whether they were actually exposed to the intervention. However, the investigators will only include participants with nonmissing data at the 6-month follow-up. In addition to the main analyses, the investigators will perform three sets of sensitivity analyses to

assess the robustness of the findings. The first set of sensitivity analyses will use an *as-treated* approach and include only people with nonmissing data at the 6-month follow-up. Individuals will be included in this analysis only if they actively participated in the interventions. For the DrugFactsBox[®]/Other CMI groups, the investigators defined active participation as viewing at least one page on the DrugFactsBox[®]/Other CMI website. For the SMART group, the investigators will define active participation as attending at least 3 of the 4 training sessions. Note that all individuals in the No SMART group will be included in the *as-treated* analyses because they will not have an opportunity to participate in any training. In the second set of sensitivity analyses, the investigators will use an *intention-to-treat* approach and impute missing data using the last-observation-carried forward method for individuals who do not complete the 6-month follow-up. In the final set of sensitivity analyses, the investigators will use as *as-treated* approach and impute missing data using the last-observation-carried forward method.

Secondary Analyses: The investigators will use the same analytic strategy to examine the effect of the intervention on 18 secondary outcomes assessed at the 6-month follow-up: Medication Self-Management Knowledge, Selective Learning, Complex Abstraction, Lesson Quality, Use of the RA Self-Management Website, Participation in the BetterChoices,BetterHealth program, Self-Efficacy, Overall Medication Satisfaction, Global Treatment Satisfaction, Medication Adherence, Objective Health Literacy, Subjective Health Literacy, Disease Activity, Illness Intrusion, Illness Distress, Global Health, Depression, and Fatigue. In these analyses, the investigators will use either logistic or linear regression, depending on the measurement properties of the outcome variable. Due to the number of endpoints examined in these secondary analyses, the investigators will use the Hochberg method to adjust for the potential inflation of Type I error.⁸⁵

Exploratory Analyses: The investigators will use the same analytic strategy to evaluate intervention effects at the 6-week and 3-month follow-ups. However, these analyses will be considered exploratory and are designed to capture any transient intervention effects that may occur.

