Statistical And Analytic Plan	
Using an intention-to-treat approach, the investigators will use logistic regression to test three hypotheses in primary analyses, with alpha (2-tailed) set at 0.05.
 
 1. Participants will be more likely to meet the criteria for Informed Decision-Making at the 6-month follow-up if they were assigned to receive written medication information via the DrugFactsBox[®] format compared to the Other CMI format. 2. Participants will be more likely to meet the criteria for Informed Decision-Making at the 6-month follow-up if they were assigned to receive gist reasoning training, delivered via the SMART Program, compared to those who were not assigned to receive this training. 3. Participants will be more likely to meet the criteria for Informed Decision-Making at the 6-month follow-up if they were assigned to receive medication information via the DrugFactsBox[®] format combined with gist reasoning training, delivered via the SMART Program, compared to individuals in the other three groups.
DATA AND SAFETY MONITORING PLAN	
The principal investigator will have primary responsibility for data quality management and ongoing assessment of safety. The principal investigator will work closely with clinical co-investigators to assess safety concerns. Because this project is associated with minimal risk, the investigators have not incorporated a formal Data and Safety Monitoring Board.

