1.3 Non-Clinical and Clinical Study Findings

The main potential risk associated with the study involves breach of confidentiality. Because the investigators are collecting information concerning patient health status and medication use, it is possible that a breach of confidentiality could affect participants' ability to obtain health insurance.

The investigators anticipate that all study participants have the potential to benefit from study participation by receiving information concerning the risks and benefits associated with different RA treatment options. Patients report having difficulty obtaining this type of information. The investigators expect participants assigned to the DrugFactBox® group combined with Gist Reasoning Training to derive the greatest benefit. In addition,

the investigators will offer all participants an opportunity to take part in the on-line BetterChoices/BetterHealth® Program free of charge. Thus, participants have the potential to benefit from participation in this chronic illness self-management program as well.

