Using FTT as our theoretical framework, the aim of this study was to evaluate the effectiveness of two interventions designed to enhance patient understanding of medication risks/benefits: the DrugFactsBox[®] format for presenting written medication information and the SMART Program to enhance gist reasoning ability. As shown in Figure 1, the investigators hypothesized that both interventions would increase: (1) patient knowledge concerning medication risks/benefits and (2) interest in obtaining additional information about illness self-management. Moreover, by improving gist reasoning ability, the investigators hypothesized that the SMART Program would work synergistically with the Drug Facts Boxes to improve patient health outcomes. Our primary outcome variable was informed decision-making, defined as making a value-consistent decision concerning DMARD use in the presence of adequate knowledge. Other intermediate and distal outcome variables are shown in Figure 1.

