6.4 Sample Size and Power

The primary outcome variable will be Informed Decision-Making, assessed at the 6-month follow-up. Our targeted sample size will be 300 (75 in each of the four study arms). Power analyses performed a priori indicated that a sample of this sample size would provide 80% power to detect a between-group difference of 25% in the percentage of participants classified as meeting the criteria for informed decision-making (e.g., 60% versus 35% among individuals assigned to the DrugFactsBox[®] versus Other CMI groups, respectively). This anticipated effect size was based on that observed in previous studies⁵⁵ and corresponds to a slightly smaller than moderate sized effect using the criteria developed by Cohen.⁸⁶ These power calculations were performed with

alpha (2-tailed) set at 0.05 and allowed for 15% attrition from baseline to final follow-up.

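### Primary Hypothesis 3 claims that the combined arm does better than the other three groups, but its only assigned test is an interaction term, which answers a different question

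*Combined protocol and SAP*

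**What the plan says.** The synopsis (Statistical and Analytic Plan) and Section 6.3 list three primary hypotheses. The third says that the DrugFactsBox arm with gist training, "delivered via the SMART Program, compared to individuals in the other three groups", is more likely to meet the Informed Decision-Making criteria at 6 months.

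The main logistic model in Section 6.3 holds baseline Informed Decision-Making and one indicator for each intervention. Interactions are tested in separate models, and one of them is assigned to the third hypothesis by name: "The first interaction will assess whether the effects of the two interventions are dependent of one another (Hypothesis 3". Also in Section 6.3: "Statistical significance will be evaluated with alpha (2-tailed) set at 0.05", and "When significant interaction terms are observed, the investigators will use stratified analyses to examine the nature of the interaction". No unconditional contrast of the combined arm with the other arms, pooled or one by one, appears anywhere.

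The background supports both ideas. Section 1.3 expects the "group combined with Gist Reasoning Training to derive the greatest benefit", which is a ranking. Section 1.4 says that "the SMART Program would work synergistically with the Drug Facts Boxes to improve patient health outcomes", which is an interaction idea, although it speaks of health outcomes. Section 6.4 claims "80% power to detect a between-group difference of 25% in the percentage of participants", with 60% v 35% for DrugFactsBox v Other CMI as the example.

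**The concern.** The hypothesis is about which arm does best. The test is about whether the effect of one intervention, on the odds-ratio scale, depends on the other. Neither statement implies the other, so the reported result for one of three primary hypotheses would not say whether it is true.

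Two errors could follow. If both interventions help and their odds ratios simply multiply, the combined arm is best, yet the interaction is null and the hypothesis would be reported as unsupported. If returns diminish, a significant result under this hypothesis would come from a negative interaction, and the plan does not say that this fails to support it. Section 6.3 also carries the same analytic strategy to 18 secondary outcomes. Hypotheses 1 and 2 are tested directly and are not affected.

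**Working it through.** **Inputs from the documents.** 300 participants, 75 per arm, 15% attrition, two-sided alpha 0.05, 60% v 35% (Section 6.4); 1:1:1:1 allocation (Section 3.2). Completers per arm: 75 × 0.85 = 63.75, taken as 64 in the simulations. The documents give no four-arm rates, so every set below is an assumption, in the order neither / DrugFactsBox only / SMART only / both.

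**The plan's own power figure.** Two-proportion z test, power = Φ{[|p1 − p2|√n − 1.96√(2p̄(1 − p̄))] / √(p1(1 − p1) + p2(1 − p2))}. With p1 = 0.60, p2 = 0.35, p̄ = 0.475, n = 63.75: (1.996 − 1.384) / 0.684 = 0.895, so power is 81.5%. The stated 80% reproduces as one arm v one arm. The comparison of all DrugFactsBox with all Other CMI participants (127.5 v 127.5) would have 98%.

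**Why the two statements differ.** The interaction is b = logit(both) − logit(DrugFactsBox only) − logit(SMART only) + logit(neither), with SE = √Σ[1/(n p(1 − p))] over the four arms. The hypothesis as worded concerns p(both) against the other three rates.

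- At 35/60/60/70: b = 0.847 − 0.405 − 0.405 − 0.619 = −0.583 (odds ratio 0.56). SE = √(17.49/63.75) = 0.524. Power is about 20%, in the negative direction. The pooled others average (35 + 60 + 60)/3 = 51.7%, so the combined arm is 18.3 points better. Power of the pooled contrast is 74%.
- At 35/35/35/60: b = 0.405 + 0.619 = 1.024 (odds ratio 2.79). SE = √(17.35/63.75) = 0.522. Power of the interaction is about 50%.

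**Simulation.** 200,000 trials per pattern, 64 per arm, no covariate. Interaction: Wald test, two-sided 0.05. Pooled: two-proportion z, 64 v 192, favourable direction. Pairwise: combined arm better than each of the three by Wald log-odds contrasts above 1.96 SE.

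| Assumed rates (%) | Interaction significant, positive | Interaction significant, negative | Pooled contrast | All three pairwise |
|---|---|---|---|---|
| 30/55/40/65 | 2.3% | 2.8% | 90.5% | 20.5% |
| 25/55/45/65 | 0.2% | 14.7% | 90.5% | 18.9% |
| 35/50/35/70 | 36.8% | 0.0% | 98.9% | 64.0% |
| 35/60/35/60 | 2.5% | 2.5% | 63.8% | 2.6% |
| 35/60/60/81 | 2.6% | 2.4% | 99.4% | 61.1% |
| 35/60/60/70 | 0.1% | 20.3% | 74.2% | 9.9% |
| 35/35/35/60 | 51.2% | 0.0% | 94.3% | 60.8% |
| 60/35/35/43.3 | 77.1% | 0.0% | 2.6% | 0.0% |

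The first four patterns keep the Section 6.4 example of 60% and 35% for all DrugFactsBox and all Other CMI participants; for the first, (55 + 65)/2 = 60 and (30 + 40)/2 = 35. The fourth shows that the wording is itself ambiguous: when only DrugFactsBox works, the pooled reading succeeds in 64% of trials and the strict reading in 3%. The last row is the reverse case: the interaction is usually positive although the combined arm is below the neither arm and equals the average of the other three.

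**Baseline adjustment.** With an assumed baseline rate of 35% and an odds ratio of 4 for the baseline covariate (40,000 trials, adjusted logistic models), 30/55/40/65 gives 2.2% positive, 2.8% negative, 92.9% pooled and 21.7% pairwise. For 25/55/45/65 the figures are 0.2%, 16.4%, 92.9% and 19.8%. The contrast between the tests does not change.

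**Can Hypotheses 1 and 2 stand in?** At 35/60/60/60 both are significant in 28% of trials (main-effects model, 40,000 trials), although the combined arm is no better than either single arm. They do not form a decision rule for Hypothesis 3.

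**The case against.** The best defence is that synergy was meant all along. The objective (synopsis and Section 2.1) asks whether gist training can increase the effectiveness of the written materials, which is effect-modification language, and Section 6.3 names the interaction as the test, so the analyst has no choice to make. This makes the synergy reading the likelier intent. It does not rescue the text: if synergy was meant, the hypothesis is misworded in both places, and Section 1.3 still points to a ranking.

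Second, the stratified analyses would yield some of the missing comparisons. SMART v no SMART within DrugFactsBox is combined v DrugFactsBox only, and DrugFactsBox v Other CMI within SMART is combined v SMART only. That is correct, but they run only after a significant interaction, the stratifying factor is not stated, and they are not set up as a test of the hypothesis.

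Third, the reverse pattern is contrived, because each intervention alone would have to lower the rate by 25 points. This is fair. It serves only to show that one statement does not imply the other; the patterns with no synergy or with diminishing returns need no unusual assumption.

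Fourth, the figure in Section 6.4 has the form of a single pairwise contrast, and two-sided tests of directional hypotheses are ordinary. Both points are true. But one pairwise comparison is not the interaction, the pooled contrast or success on all three, and although the wording does give a direction, the plan should still say that a negative interaction does not support it.

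**Conclusion.** The concern holds and must be fixed. Following Section 6.3 exactly answers a different question from the one that the third primary hypothesis states. In the two plausible patterns where effective interventions show no synergy or diminishing returns while the 60% and 35% margins hold (30/55/40/65 and 25/55/45/65), a positive significant interaction appears in about 2% of trials or fewer, against about 90% for the pooled contrast. The size of the gap depends on assumed four-arm rates, 64 completers per arm and, for the main figures, no covariate. That the two statements are not equivalent depends on none of these. The 80% in Section 6.4 is sound as an arm-v-arm figure but is not the power of Hypothesis 3 under any of its readings. Hypotheses 1 and 2, their estimates and the randomisation are unaffected.

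**What to change.** Before 6-month outcomes are analysed by arm, choose one reading and make the synopsis and Section 6.3 agree.

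- **Pooled ordering.** Combined arm v the other three pooled, adjusted for baseline Informed Decision-Making, favourable direction required. State that this can succeed when only DrugFactsBox works (about 64% at 35/60/35/60), so it does not show that the combination beats DrugFactsBox alone.
- **Strict ordering.** Combined arm better than each of the three arms, with all three contrasts required at two-sided 0.05 in the favourable direction. Because all must succeed, no multiplicity adjustment is needed within this hypothesis.
- **Synergy.** Reword the hypothesis to say that the DrugFactsBox odds ratio is larger with SMART than without, keep the interaction test, and state that only a positive interaction supports it.

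Under either ordering option, report the interaction separately as the synergy question. In every case add to Section 6.4 the power of the chosen test under stated rates for the four arms.

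The cost is wording in two places, one contrast, three contrasts or a reworded hypothesis, and one power statement; no new patients or data. The downside is that the stated power may fall well below 80% for the strict and synergy options (at 35/35/35/60, about 61% and 50%). On timing, the Appendix Table 1 reports a reliability of 0.36 for Medication Self-Management Knowledge, a measure listed only at 6 months, so some 6-month data may already exist; the documents do not say whether any were analysed by arm. If they were, an ordering test added now would be post hoc, whereas the synergy option keeps the test already named.

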15 APPENDIX

Figure 1. Conceptual Framework

[figure not shown]

Table 1. Summary of study measures

Variable	Time Assessed	Data Collection Instrument	Range	Baseline Alpha
Knowledge	B, 6W, 3M, 6M	Telephone Interview	0 to 100	0.84
Values	B, 6W, 3M, 6M	Self-Administered Questionnaire	-15 to +15	0.67
DMARD Usage	B, 6W, 3M, 6M	Self-Administered Questionnaire	0=Not using any DMARDS 1=Using 1+ DMARDS	NA
Informed Decision-Making	B, 6W, 3M, 6M	Composite measure based on Knowledge, Values and DMARD Usage	0=Did not meet criteria 1=Met criteria	NA
Gist Reasoning Ability:				
Complex Abstraction	B, 6W, 3M, 6M	Self-Administered Questionnaire†	0 to 8	NA
Lesson Quality	B, 6W, 3M, 6M	Self-Administered Questionnaire†	0 to 5	NA
Selective Learning	B, 6W, 3M, 6M	Telephone Interview	0 to 264	0.67
Verbatim Recall	6W	Telephone Interview	0 to 2	0.14††
Medication Self-Management Knowledge	6M	Telephone Interview	0 to 100	0.36

Variable	Time Assessed	Data Collection Instrument	Range	Baseline Alpha
Information Seeking:				
Use of RA Self-Management Website	6M	NA	0=Never accessed website 1=Accessed website 1+ times	NA
Participation in BetterChoices, Better Health	6M	NA	0=Did not participate in all 6 sessions 1=Participated in all 6 sessions	NA
Treatment Satisfaction:				
Global	B, 6W, 6M	Self-Administered Questionnaire	0 to 100	0.83
Effectiveness	B, 6W, 6M	Self-Administered Questionnaire	0 to 100	0.90
Side-Effects	B, 6W, 6M	Self-Administered Questionnaire	0 to 100	0.82
Convenience	B, 6W, 6M	Self-Administered Questionnaire	0 to 100	0.86

Variable	Time Assessed	Data Collection Instrument	Range	Baseline Alpha	
Satisfaction with Medication Information: Overall					
	B, 6W, 6M	Self-Administered Questionnaire	0 to 17	0.88	
	Actions	B, 6W, 6M	Self-Administered Questionnaire	0 to 9	0.78
Problems	B, 6W, 6M	Self-Administered Questionnaire	0 to 8	0.85	
Arthritis Self-Efficacy	B, 6W, 6M	Self-Administered Questionnaire	0 to 100	0.87	
Illness Intrusiveness: Overall					
	B, 6M	Self-Administered Questionnaire	0 to 100	0.90	
	Relationships	B, 6M	Self-Administered Questionnaire	0 to 100	0.85
	Instrumental	B, 6M	Self-Administered Questionnaire	0 to 100	0.71
Intimacy	B, 6M	Self-Administered Questionnaire	0 to 100	0.82	
Health Distress	B, 6M	Self-Administered Questionnaire	0 to 5	0.91	

Variable	Time Assessed	Data Collection Instrument	Range	Baseline Alpha
Depression	B, 6M	Self-Administered Questionnaire	T-Score: Mean =50, SD=10 in reference population	NA

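### Section 6.3 does not say that each secondary outcome is adjusted for its own baseline; read literally, 15 of the 18 would be adjusted only for baseline Informed Decision-Making

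*Combined protocol and SAP*

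**What the plan says.** Section 6.3 (Primary Analyses) sets out the model: "The regression model will control for Informed Decision-Making at baseline", together with "indicator variables for each intervention indexing whether the participant was assigned to SMART Training" and the matching indicator for DrugFactsBox. No other baseline covariate is named. For the primary outcome this covariate is the outcome's own baseline value. Separate models test interactions, two of which ask "whether the effects of each intervention varies as a function of whether participants met the criteria for Informed Decision-Making at baseline"; a significant interaction leads to stratified analyses.

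Section 6.3 (Secondary Analyses) then says: "The investigators will use the same analytic strategy to examine the effect of the intervention on 18 secondary outcomes assessed at the 6-month follow-up". Two changes from the primary analysis are stated. One is the form of the model ("the investigators will use either logistic or linear regression, depending on the measurement properties of the outcome variable"); the other is a Hochberg adjustment for the number of endpoints. Covariates are not mentioned. The exploratory 6-week and 3-month analyses refer back to the same strategy in the same way.

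Table 1 (section 15) gives a baseline assessment for 15 of the 18 listed outcomes. The other three appear with a 6-month time point only: "Medication Self-Management Knowledge 6M", "Use of RA Self-Management Website 6M" and "Participation in BetterChoices, Better Health 6M".

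**The concern.** The wording allows two models for each of 15 outcomes. If the primary model is carried over unchanged, 6-month fatigue, depression, disease activity, self-efficacy and the rest are adjusted for a binary decision flag that may have little to do with them, while their own baseline scores go unused. That gives away precision the trial has already paid for, in a family that also bears a multiplicity adjustment over 18 endpoints.

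If instead the intention is to adjust each outcome for its own baseline, the rule is not written down and does not cover three outcomes. Two analysts following 6.3 could then produce different p-values for up to 15 outcomes, and the Hochberg procedure would act on whichever set was chosen. The same uncertainty applies to the baseline variable in the intervention-by-baseline interactions.

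**Working it through.** **Count from Table 1.** With baseline: Selective Learning, Complex Abstraction, Lesson Quality, Self-Efficacy, Overall Medication Satisfaction, Global Treatment Satisfaction, Medication Adherence, Objective and Subjective Health Literacy, Disease Activity, Illness Intrusion, Illness Distress, Global Health, Depression and Fatigue. That is 15. Without baseline: Medication Self-Management Knowledge, website use and BetterChoices participation. That is 3. I have matched Overall Medication Satisfaction to Satisfaction with Medication Information (Overall), Illness Distress to Health Distress, and Illness Intrusion to Illness Intrusiveness (Overall).

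**The plan's own figure.** Section 6.4 states 300 participants (75 per arm), 80% power, 60% versus 35%, two-sided alpha 0.05 and 15% attrition.
- n per arm = [1.960·√(2·0.475·0.525) + 0.842·√(0.60·0.40 + 0.35·0.65)]² / 0.25², which rounds up to 62.
- 62/0.85 rounds up to 73 per arm, or 292 in total. With 75·0.85 = 63.75 per arm, power is 81.5%.

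The stated figure reproduces. It concerns the primary outcome; no power is stated for secondary outcomes, so what follows is illustrative.

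**Precision under the literal reading.** Inputs:
- Completers per level of one intervention, pooling two arms: 2·75·0.85 = 127.5 (section 6.4).
- Correlation r between baseline and 6-month score: not in the documents; assumed 0.3 to 0.7.
- Baseline Informed Decision-Making assumed uncorrelated with the outcome.

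Formulas:
- Standard error with own baseline, relative to without: √(1 − r²).
- Detectable difference without own baseline: (1.960 + 0.842)·√(2/127.5) = 0.351 SD. With own baseline, multiply by √(1 − r²).
- Unadjusted sample size giving the same precision: 255/(1 − r²).

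| r | √(1 − r²) | SE cut | Detectable difference (SD) | Power for 0.30 SD | Equivalent unadjusted N |
|---|---|---|---|---|---|
| none | 1.000 | – | 0.351 | 66.8% | 255 |
| 0.3 | 0.954 | 5% | 0.335 | 70.9% | 280 |
| 0.5 | 0.866 | 13% | 0.304 | 79.0% | 340 |
| 0.6 | 0.800 | 20% | 0.281 | 84.9% | 398 |
| 0.7 | 0.714 | 29% | 0.251 | 91.8% | 500 |

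These figures use alpha 0.05 before any Hochberg adjustment.

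**Sensitivity to the decision flag.** If baseline Informed Decision-Making correlates 0.2 with an outcome, it reduces that outcome's standard error by 1 − √(1 − 0.04), about 2%. Replacing it with own baseline at r = 0.5 then cuts the standard error by 1 − √(0.75/0.96), about 12%. If both correlations were 0.3, replacement would gain nothing.

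**Low-reliability measures.** Objective Health Literacy uses one version at baseline and the other at 6 months (section 5.1), with alphas of 0.60 and 0.49 (Table 1). If alpha is taken as reliability, the observed correlation is capped near √(0.60·0.49) = 0.54, so the standard error can fall by at most 1 − √(1 − 0.294), about 16%. The 0.6 and 0.7 rows do not apply to it. Gist reasoning uses a different text and Selective Learning different word lists at each visit, so their correlations may also be lower.

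**The case against.** The best reply is that the plan speaks of a strategy, not of identical covariates. In the primary model the covariate is the baseline of the outcome being analysed. Carrying that principle to fatigue means adjusting for baseline fatigue. The plan already lets the form of the model vary by outcome, and Table 1 collects the baselines that would be needed. If that is the intention, no precision is lost.

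This reading is fair and cannot be excluded. A reader might infer that 15 outcomes definitely will not be adjusted for their own baseline; the documents do not support so firm a statement. Nor do they settle the matter the other way. The literal model can be fitted to all 18 outcomes, whereas the own-baseline rule has no covariate for three of them and no exception is made. The interaction tests and stratified follow-up are also written around a yes/no baseline status, and no rule is given for a baseline score.

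Two further objections stand in full. The correlations are assumptions, and at 0.3 the gain is small. The documents set no power target for secondary outcomes, so no stated figure is contradicted.

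**Conclusion.** The point holds as a gap in specification: section 6.3 does not state the baseline covariate for any secondary outcome. Read literally, it omits own-baseline adjustment for 15 of 18. On that reading, and for continuous outcomes, the standard error is larger than it need be: own-baseline adjustment would cut it by about 5% at r = 0.3 and 29% at r = 0.7. On the own-baseline reading the loss is nil, but the rule is unwritten and incomplete.

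Two stronger conclusions should not be drawn. The first is bias: allocation is randomised, so omitting a baseline costs precision and leaves chance imbalance in the estimate, but does not shift it systematically. The second is that every secondary interval is affected: three outcomes have no baseline of their own to omit. The primary analysis is untouched, since it already adjusts for its own baseline. The change is worth making because it uses data already scheduled for collection and fixes the model before results are seen.

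**What to change.** In section 6.3, Secondary Analyses, state:
- that each of the 15 secondary outcomes measured at baseline is modelled with its own baseline value as a covariate, and whether this replaces or is added to baseline Informed Decision-Making;
- that Medication Self-Management Knowledge, website use and BetterChoices participation keep baseline Informed Decision-Making or take another named covariate (the baseline Knowledge score is an option for the first, not a necessity);
- which baseline variable enters the intervention-by-baseline interactions, and how a significant interaction is examined when that variable is a score.

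Say also whether the same rule applies to the 6-week and 3-month exploratory analyses. The cost is a few sentences, agreed before the 6-month data are analysed; no new data or visits are needed.
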